We aim to conduct a single-center randomized controlled trial to measure the impact of physical activity through virtual reality video games on the motor and cognitive performance of youth with MS. Through such a home-exercise program coupled with patient online behavior counseling, we hypothesize that we can significantly impact subjective and objective measures of disease disability in this MS age population.

Objectives

Primary objective: to assess the impact of a virtual reality video (VR) game exercise program on **objective cognitive assessments in youth with MS** (measures outlined below). The **null hypothesis** for this study is that there is no difference in the **Brief Cognitive Assessment for MS** in cognitive disability of youth with MS between those enrolled in a 6-month VR active video game program and those with routine follow-up care. The alternative hypothesis is that there is a difference in measures of cognitive disability between the two groups (two-sided hypothesis).

Secondary objectives:

- To determine the impact of VR physical activity on subjective measures of cognitive, physical and psychosocial disability in youth with MS
- To determine the impact of VR physical activity on the 6-Minute Walk Test (6MWT).

- To determine the number of clinical relapses and new T2 MRI lesions (brain)
- To determine the **safety** of implementing a VR active video game program at home
- To evaluate the effect of VR exercise programs on overall behavior towards physical activity and health promotion in youth through self-report questionnaires

Study Design

- **Single-center, single blinded, randomized controlled trial** comparing a 6-month VR active video game intervention with standard management of physical activity in youth with MS.
- Each participant will be randomly allocated to either the intervention group or the control group for a **period of 6-months** with pre- and post- assessments performed at onset, 3 months, 6 months and 12 months follow-up.
- The study will be conducted over one year with 6 months of intervention. Each group will include 12 subjects (**total subjects = 24**).
- The Microsoft VR active game program will consist of 3 weekly sessions of 45 minutes each combining 3 different types of exercise (cardiovascular and strength with 'Box VR', flexibility with 'Beat Saber', coordination with 'The Climb').

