- **Subjective assessments** will be distributed to all participants (exercise intervention group and control group) in weeks 1 and 12 of study enrollment, and at 6-month and 12-month follow-up. The time allocated to complete these assessments is estimated to be 15-20 minutes for each visit. These will include:
 - **Multiple Sclerosis Impact Scale-29 (MSIS-29)**: 29-item self-report measuring the physical and psychological impact of MS from the patient's perspective during the previous 2 weeks.
 - **Modified Fatigue Impact Scale (MFIS)**: 21-item self-report measuring the impact of fatigue on physical, cognitive and psychosocial aspects of MS during the previous 4 weeks.
 - **Hospital Anxiety and Depression Scale (HADS)**: 14-item self-report measuring the degree of anxiety and depression in participants during the previous week.
- An MS specialist will perform a pre- and post- **objective motor assessment** during a routine clinic visit at the time of study enrollment, at 6 months and 12 months follow-up. This assessment will include:
 - **Six Minute Walk Test (6MWT)**: the participant is instructed to walk for six minutes as quickly and safely as possible and the distance covered will be recorded. This test has demonstrated excellent test-retest reliability and validity among people with mild to moderate MS²³.
- Study personnel will collect assessments during routine clinic visits using allocated forms that will be identifiable by date and subject study code number. An investigator blinded to group allocation will subsequently analyze the data.

Budget and financing

- This study has funding from Microsoft and from a private sponsor.
- Cost of VR headset and motion controllers from Microsoft : model Samsung HMD Odyssey+ Windows (\$199.00 per unit, total of 15 units for the intervention group = \$2'761.12)
- The Windows Mixed Reality headsets are compatible with a PC that will run Windows 10 Fall Creators Update, requiring no further participant equipment.
- Cost of the 3 VR video games: Box VR \$19.99, Beat Saber \$19.99, The Climb \$9.99 (downloaded from STEAM stores) – total of \$49.97 per subject, total of \$600 for the intervention group.
- Additional funding is also available with assistance from Microsoft for software to support minimum system requirements for the selected VR exercise games.

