- The subjective assessments will be mailed to the participants or given when seen in clinic. Study staff will perform the 6MWT at the time of a routine clinic visit and will require no additional costs.
- The three cognitive assessments per subject will be carried out by a qualified neuropsychologist or neurologist and will be performed at the time of a routine clinic visit.

Data and Safety Monitoring

- During the course of study participation, subjects might experience an adverse event related to the physical activity or to their underlying MS. These events might include falls, musculoskeletal injuries, neurological symptoms suggestive of a clinical relapse, or any other physical or psychological cause of distress. These events will be documented by participant self-reports and contacting study personnel. They will be graded from 1 to 3 according to their degree of severity with 1 = mild, no interference with daily activities, 2 = moderate, some interference with daily activities and 3 = severe, significant interference with daily activities and requiring medical intervention.
- The research team will perform a **periodic review of adverse events** recorded once every 2 months as well as an assessment of adherence to the exercise programs and any other concerns raised by the research team or the participants.
- In the event of a clinical relapse or worsening of a participant's neurological symptoms, the research team will promptly inform the MS specialist in charge of that participant's care. Subject's participation in the intervention group will cease.

Statistics

- Statistical analysis will be performed using the software program **Stata version 15**.
- Descriptive numerical or graphical summaries will be used for demographic and clinical characteristics of the sample population at baseline. Independent samples t-tests and chi-square tests will be done to assess differences between intervention and control groups on pre-trial and post-trial assessments. Only participants who completed the 6-month exercise program will be included in the analysis of the intervention group but missing data will be noted. Paired sample t-tests and chi-square tests will be conducted to determine differences in pre-trial and post-trial assessments within each group. If data reveals a skewed distribution, Kruskall Wallis tests will be used for continuous variables. All tests will be conducted using an alpha = 0.05 level of statistical significance.

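### Separate post-trial t-tests with missing data only noted can bias the month-6 comparison if dropout differs by arm; an all-visit mixed model is a modest, cheap improvement, mainly for the questionnaires

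*Combined protocol and SAP*

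**What the plan says.** On the between-arm comparison, the Statistics section reads: "Independent samples t-tests and chi-square tests will be done to assess differences between intervention and control groups on pre-trial and post-trial assessments". Within arms it reads: "Paired sample t-tests and chi-square tests will be conducted to determine differences in pre-trial and post-trial assessments within each group". Kruskal-Wallis is the fallback for skewed data. Nothing there models repeated measurements, adjusts for baseline, imputes, or tests sensitivity to missing data.

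On incomplete outcomes, the same section limits the intervention arm to those who finished the 6-month program and adds that "missing data will be noted". A later bullet keeps all randomized controls but only those intervention participants who finished 12 weeks, and says dropouts will be recorded. No expected dropout rate is given.

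On timing, Study Procedures gives MSIS-29, MFIS and HADS to both arms "in weeks 1 and 12 of study enrollment, and at 6-month and 12-month follow-up". It places BICAMS and the 6MWT at enrollment, 6 months and 12 months. Study Design differs: it puts subjective and objective assessments at 3 months as well, and describes pre- and post-assessments at onset, 3, 6 and 12 months. Post-trial is not tied to a named visit.

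Under Data and Safety Monitoring, a relapse or neurological worsening ends participation in the intervention group. The text does not say whether follow-up assessments continue.

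**The concern.** A t-test at one visit can use only people who have a score at that visit, and the rank-based fallback has the same limit. Keeping all randomized controls in the analysis set does not help, because no method is given for including a control whose score is missing. Someone who leaves between months 3 and 6 has already supplied a month-3 questionnaire score, but the month-6 test ignores it. Someone who misses only month 6 may have a month-12 score, which is ignored too.

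The risk is bias when the people who leave one arm differ in their scores from those who leave the other. That is plausible here because the completer restriction and the relapse exit both act on the intervention arm only, and that arm alone carries three 45-minute sessions a week. If the more fatigued VR participants are the ones who leave, those who remain look better at month 6 even when the program does nothing.

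**Working it through.** There is no figure in the plan to reproduce: "Each group will include 12 subjects" comes without a power, effect size, SD or dropout rate. The inputs from the documents are 12 per arm, a "two-sided hypothesis", alpha 0.05, and questionnaire visits at months 0, 3, 6 and 12. Everything else is assumed.

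**Assumed inputs**
- Scores have SD 1, higher is worse, and there is no true effect.
- Any two visits correlate at r = 0.5 to 0.8.
- Between months 3 and 6, a quarter to a third of the VR arm leaves. The log-odds of leaving rise by 1.5 per SD of the month-3 score.
- Controls do not leave.

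**Step 1: selection.** Let m be how far the mean month-3 score of VR stayers lies below that of the whole VR arm. Numerical integration of the logistic model gives m = 0.277 SD when 25% leave and m = 0.360 SD when one third leave.

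**Step 2: planned t-test.** The large-sample bias at month 6 is r × m.
- Low end: 0.5 × 0.277 = 0.14 SD.
- High end: 0.8 × 0.360 = 0.29 SD.

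**Step 3: baseline-adjusted complete cases.** Given baseline, the month-6 score depends on the month-3 score with coefficient r/(1 + r). The part of the month-3 shift that baseline does not explain is m(1 − r²). The bias is their product, r(1 − r)m.
- Low end (r = 0.8, 25% leave): 0.16 × 0.277 = 0.04 SD.
- High end (r = 0.5, one third leave): 0.25 × 0.360 = 0.09 SD.

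Baseline adjustment alone therefore removes a fraction r, that is 50% to 80%, of the t-test bias.

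**Step 4: all-visit model.** It conditions on the month-3 score, which is what drives leaving under these assumptions, so the bias is about 0.

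**Step 5: same mechanism in both arms.** Both means shift by r × m, and r × m − r × m = 0.

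**Simulation at 12 per arm**

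| Analysis | Month-6 bias, VR-only dropout |
|---|---|
| Planned t-test | 0.13 to 0.30 SD |
| Baseline-adjusted complete cases | 0.04 to 0.09 SD |
| All-visit model | about 0 |

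The all-visit result here treats the covariance as known. With compound symmetry estimated by REML and about 28% VR-only dropout, the three biases are 0.13 to 0.25 SD, about 0.06 SD, and within 0.02 SD of zero.

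In a separate run with 25% VR-only dropout and slopes of 1 or 2 per SD, the completer t-test has a true type I error of 5.7% to 8.7% against a nominal 5%.

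**Precision.** With random 20% dropout in both arms, the all-visit standard error is 14% to 41% below that of the t-test, but only about 3% to 6% below baseline-adjusted complete cases.

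**The case against.** Five points can fairly be made against this.

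- **The bias is conditional.** A reader might infer that dropout linked to earlier scores biases the comparison in itself. The documents do not support that: they give no dropout rate, and the bias vanishes if the same mechanism acts in both arms. What stands is that it can arise, and that two features of the plan press on one arm only.
- **Most of the 0.13 to 0.30 SD belongs to other faults.** It reflects the completer restriction and the lack of baseline adjustment. This is correct. The part specific to this point is 0.04 to 0.09 SD, against a sampling SD of 0.28 to 0.42 and a difference of about 1.20 SD needed for 80% power at 12 per arm.
- **Month 3 may be tested after all.** It is tempting to say that the week-12 questionnaires enter no analysis. Study Design counts month 3 among the pre- and post-assessments, so a separate month-3 t-test is a fair reading. It would still not inform a missing month-6 score.
- **The primary outcome is less affected.** Under Study Procedures BICAMS has no month-3 score, so a participant who leaves after enrollment has only the baseline score to contribute. The gain for BICAMS is smaller and was not quantified. Study Design conflicts on whether month-3 objective tests exist.
- **The near-zero bias of the model is partly built in.** Dropout was generated from an observed score. When it depends on the unseen month-6 score, the all-visit model is still biased by 0.09 to 0.21 SD, against 0.12 to 0.23 SD for baseline-adjusted complete cases. A relapse need not show in a month-3 questionnaire. This stands, and it is why a sensitivity analysis is needed.

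**Conclusion.** The point holds in a limited form. The plan states no method for missing outcomes, and its tests leave unused scores that will already have been collected. Under differential dropout this can shift the month-6 difference by about 0.13 to 0.30 SD. The part that remains after keeping all randomized participants and adjusting for baseline is 0.04 to 0.09 SD of bias and about 3% to 6% of standard error, and these figures apply to the secondary questionnaires.

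The sizes rest on assumed dropout, correlation and dropout slope, on missingness explained by observed scores, and on reading post-trial as month 6. The change is worth making because it needs no new data and a trial of 24 can ill afford to leave scores unused. The evidence does not show that the result will be biased, or that BICAMS is affected to the same degree.

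**What to change.** 1. Define post-trial as a named visit, with month 6 for the main comparison. Reconcile Study Design with Study Procedures on whether objective tests are done at 3 months.
2. Replace the separate post-trial t-tests with one linear mixed model per continuous outcome, using every available score from all randomized participants. Specify a common baseline mean, visit and visit-by-arm terms, REML, and Kenward-Roger degrees of freedom. Fix the covariance structure before outcomes are analysed; compound symmetry is a reasonable choice at n = 24.
3. Report the month-6 arm difference with its 95% CI, and take month 12 from the same model.
4. Replace the statement that "missing data will be noted" with a table of missing scores by arm and visit, and add a simple delta-shift sensitivity analysis for data missing not at random.

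The cost is SAP wording and slightly more analysis work, with no new visits, data or participants. The price is reliance on the missing-at-random and covariance assumptions, which 24 participants can check only weakly.

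### Unless McNemar's test was meant, the chi-square tests planned for within-group pre/post differences do not suit paired data; the impact is limited because no categorical pre/post outcome is defined

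*Combined protocol and SAP*

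**What the plan says.** The Statistics section handles the two kinds of comparison in parallel sentences. Between arms: "Independent samples t-tests and chi-square tests will be done to assess differences between intervention and control groups on pre-trial and post-trial assessments". Within arms: "Paired sample t-tests and chi-square tests will be conducted to determine differences in pre-trial and post-trial assessments within each group". The t-test changes from independent to paired, but the categorical test carries the same name in both places. Neither McNemar's test nor any other paired categorical test is named anywhere. The only non-parametric fallback is Kruskal-Wallis for skewed continuous variables, which is also a test for independent samples.

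On numbers, the Study Design section states "Each group will include 12 subjects", and the Statistics section adds "Only participants who completed the 6-month exercise program will be included in the analysis of the intervention group". Twelve pairs is therefore a ceiling for each within-arm test. On the threshold: "All tests will be conducted using an alpha = 0.05 level of statistical significance".

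**The concern.** Pearson's chi-square test assumes independent observations. Pre and post values from one person are not independent, and the question within an arm is whether people changed. The plan does not say how the table would be laid out, and the two obvious layouts go wrong in opposite directions. One can call a perfectly stable group significantly different; the other seldom rejects when values are positively correlated. Two analysts following the same sentence could reach opposite conclusions from the same data, which pre-specification is meant to prevent.

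**Working it through.** The plan gives no figure to reproduce: it states no event rate, pre/post correlation, effect size or power for this analysis.

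**Inputs from the documents:** at most 12 pairs per arm (Study Design, Statistics); alpha 0.05 (Statistics).

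**Assumptions for illustration:** a yes/no outcome, true proportion p from 0.3 to 0.5 at both times, within-person correlation ρ from 0 to 0.7.

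**1. Nobody changes.** Let a = affected both times, b = affected before only, c = affected after only, d = neither. Take a = 6, b = 0, c = 0, d = 6.

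- Cross-table of pre against post: χ² = n(ad − bc)² / [(a+b)(c+d)(a+c)(b+d)] = 12 × 36² / 6⁴ = 12.0 on 1 df, p = 0.0005. Yates' correction (p = 0.004) or Fisher's test (p = 0.002) does not cure this, because the table still tests association.
- Stacked table (6/12 before, 6/12 after, as two samples): χ² = 0, p = 1.0.
- McNemar: b + c = 0 discordant pairs, p = 1.0.

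**2. Real change.** Take a = 3, b = 6, c = 0, d = 3, so six people improve and none worsens.

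- Cross-table: χ² = 12 × (9 − 0)² / (9 × 3 × 3 × 9) = 972/729 = 1.33, p = 0.25.
- Exact McNemar: 2 × 0.5⁶ = 0.031.

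So the cross-table can also miss a change that is there.

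**3. Rejection rates with no true change.** The cell probabilities are p₁₁ = p² + ρp(1 − p), p₁₀ = p₀₁ = p − p₁₁ and p₀₀ = 1 − p₁₁ − 2p₁₀. For p = 0.4 and ρ = 0.5: p₁₁ = 0.16 + 0.5 × 0.24 = 0.28, p₁₀ = p₀₁ = 0.12, p₀₀ = 0.48. Summing the multinomial probability of every 2×2 paired table with n = 12 that gives p < 0.05 yields, for p = 0.4:

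| ρ | Cross-table χ² | Stacked χ² | McNemar, asymptotic | McNemar, exact |
|---|---|---|---|---|
| 0 | 5.58% | 5.94% | 4.95% | 1.25% |
| 0.3 | 18.91% | 2.46% | 4.74% | 0.46% |
| 0.5 | 42.89% | 0.87% | 3.00% | 0.12% |
| 0.7 | 74.51% | 0.14% | 0.88% | 0.01% |

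The assumed proportion matters little: at ρ = 0.5 the cross-table rejects in 42.8% of trials for both p = 0.3 and p = 0.5, and the stacked table in 0.7% and 1.0%.

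**4. Why the stacked table is conservative.** The test takes the variance of the difference in proportions as 2p(1 − p)/n, but for paired values it is 2p(1 − p)(1 − ρ)/n. At ρ = 0.5 the assumed variance is twice the true one.

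**The case against.** The strongest reply is that the words paired sample at the head of the within-group sentence govern both nouns, in deliberate contrast to the independent-samples sentence. A paired chi-square test is McNemar's, and the plan would then be right. This reading is possible, so the point must be stated conditionally. It is not secure, because the same bare term serves for independent groups and McNemar is never named.

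Second, no affected outcome can be pointed to. The measures with both a pre and a post value (the BICAMS subtests, MSIS-29, MFIS, HADS and the 6MWT) are described as scores or a distance, with no cut-off. This stands and limits the impact. A reader might infer that relapses, falls and graded adverse events would be mis-tested. The documents do not support that: these are events recorded during the study, with no pre-trial value, so the within-group test cannot be run on them.

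Third, the false-positive result belongs only to the cross-table. The stated aim is to find differences, which fits the stacked table at least as well, and there the stable group gives p = 1.0. This also stands: false-positive inflation is possible under the plan, not established.

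Fourth, under the stacked layout the fault is conservatism, and exact McNemar is more conservative still (0.12% against 0.87% at ρ = 0.5). That is correct. It is a reason to allow mid-p, not to keep a test that assumes independence.

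**Conclusion.** The point holds in conditional form. If McNemar was not intended, the plan names an invalid test for any categorical pre/post outcome. With 12 pairs and no true change, the error rate at the 5% level is 43% in one layout and 0.9% in the other, at an assumed correlation of 0.5 and proportion of 0.4. At ρ = 0.3 the figures are 19% and 2.5%; at ρ = 0.7, 75% and 0.1%. All of these rest on assumed values, because the documents give none, and on 12 pairs, which is the maximum.

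Two further inferences should be resisted. One is that the trial's main result is compromised: the primary hypothesis is a between-group BICAMS comparison, on which within-arm categorical tests do not bear. The other is that the between-arm chi-square test must also be replaced by an exact test: with 12 per arm its true size is 0.2% to 6.4% for event rates from 0.05 to 0.5, so that choice is a trade-off and not an error. What remains is a correction worth making, small in consequence and in cost.

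**What to change.** In the within-group sentence of the Statistics section, replace chi-square tests with McNemar's test (exact or mid-p) for yes/no items and the Wilcoxon signed-rank or sign test for ordered categories. Beside it, list the categorical pre/post outcomes to which it applies, with any cut-offs. If there are none, delete the commitment to categorical within-group tests. If McNemar was meant all along, naming it settles the matter.

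The cost is one sentence and a short list, with no change to visits, data collection or sample size. The downside is conservatism. With 12 pairs, exact McNemar rejects in at most 1.4% of null trials over the assumed range. For an assumed fall from 50% to 20% affected with ρ = 0.5, it detects the change in 12% of trials, against 29% for the stacked chi-square and 51% for asymptotic McNemar. Mid-p reduces the loss. For five changes in one direction and none in the other, exact p = 2 × 0.5⁵ = 0.063; subtracting the probability of the observed split, 0.5⁵ = 0.031, gives mid-p = 0.031. Whether exact or mid-p is used should be fixed before the data are seen.

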- Participants will be **randomly allocated in blocks** to either the intervention or control group, and the allocation group will be **concealed from the study personnel** that are analyzing the data.

Study Procedures

- Subjects in the intervention group will receive a Samsung Windows Mixed Reality headset with motion controllers that links to their PC/laptop. They will be given 3 different VR video games (Box VR, Beat Saber and The Climb) at onset. They will be instructed to play a minimum of 3 sessions per week, one session on each game, for the first 3 months. They will have the possibility of dropping one game for the remaining 3 months but maintaining a minimum of 3 sessions per week. Each session will last 45 minutes. They may play more than 3 sessions per week but will be required to document additional time.
- **Exercise logs** will be provided to document weekly sessions for monitoring adherence. Participants in both groups will be asked to document any sport activities performed during the study period, with an estimate of duration per week and type of activity, to account for physical activity done outside of the active intervention. This will be recorded during the 6-month intervention period.
- The intervention group will also receive two **education discussion sessions** on the benefits of exercise for people with MS. The investigator MS specialists will conduct these sessions either by phone or at the time of a clinic visit and will also discuss difficulties encountered by participants with adherence.
- A neuropsychologist or MS specialist will perform an **objective cognitive assessment** at the time of enrollment, at 6 months and at 12 months follow-up, consisting of the **Brief International Cognitive Assessment for MS (BICAMS)**, which includes three subtests:
 - **Symbol Digit Modalities Test (SDMT)**, a measure of sustained attention, working memory and information processing speed
 - **California Verbal Learning test – II (CVLT-II)**, a measure of verbal memory (immediate recall) including the first 5 recall trials
 - **Brief Visuospatial Memory Test (BVMT) - Revised**, a measure of visuo-spatial learning and delayed recall, using the first 3 recall trials

The battery takes 15 min to complete, requires no specialist equipment and no specialist expertise in cognitive assessment.

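### Paired tests within each arm have the same standing as the between-arm tests and are the only listed tests of change; rest conclusions on a baseline-adjusted between-arm comparison

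*Combined protocol and SAP*

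**What the plan says.** The Objectives section frames the question between arms. The null is no difference on the cognitive battery between the VR programme and routine care, and the two-sided alternative is that "there is a difference in measures of cognitive disability between the two groups".

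The Statistics section lists two kinds of test:

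- Between arms: "Independent samples t-tests and chi-square tests will be done to assess differences between intervention and control groups on pre-trial and post-trial assessments".
- Within arms: "Paired sample t-tests and chi-square tests will be conducted to determine differences in pre-trial and post-trial assessments within each group".

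One level covers both: "All tests will be conducted using an alpha = 0.05 level of statistical significance". No test is named as primary, and the within-arm tests are not called descriptive. The between-arm tests are on pre-trial and post-trial scores; no between-arm comparison of change or of baseline-adjusted scores is named.

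Study Procedures schedules an objective cognitive assessment "at the time of enrollment, at 6 months and at 12 months follow-up, consisting of the" BICAMS, with three subtests (SDMT, CVLT-II, BVMT-R). Budget and financing agrees on the count: "The three cognitive assessments per subject will be carried out by a qualified neuropsychologist or neurologist". Alternate forms and practice effects are not mentioned.

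**The concern.** Anything that moves scores upward over six months in both arms, such as familiarity with the tests or a time trend, drops out of a comparison between randomised arms. It does not drop out of a paired test in one arm, which asks only whether mean change is zero.

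The pattern of a significant gain under VR and none under control is therefore not a test of the trial's hypothesis. It can arise by chance when both arms gain equally. The plan gives no rule for reading it, and the paired tests are the only place where change is tested. With 12 per arm, a non-significant between-arm result beside a significant within-arm one is a realistic outcome, and the reader would not know which the plan meant to carry the conclusion.

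**Working it through.** **From the documents.** "Each group will include 12 subjects", so 2 × 12 = 24, which matches the stated total. No effect size, SD, power, retest gain or test-retest correlation for BICAMS is given, so there is no other figure to reproduce. Alpha is 0.05, two-sided for the between-arm alternative; I apply the same to the paired tests. I take post-trial to mean 6 months.

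**Assumed, not in the documents.** No VR effect; the same retest gain g (in baseline SDs) in both arms; pre-post correlation r = 0.7.

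**Step 1: one subtest, VR arm.** The standardised mean change is dz = g / √(2(1 − r)) = g / √0.6. The paired t has noncentrality dz × √12 and critical value 2.201 on 11 df. The probability of a significant gain is the upper tail of the noncentral t.

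| g | dz | dz × √12 | P(significant gain), n = 12 |
|---|---|---|---|
| 0 | 0 | 0 | 2.5% |
| 0.1 | 0.129 | 0.447 | 6% |
| 0.2 | 0.258 | 0.894 | 13% |
| 0.3 | 0.387 | 1.342 | 23% |
| 0.5 | 0.645 | 2.236 | 53% |

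At r = 0.8 the last three become 17%, 32% and 70%. The Statistics section limits the VR arm to completers. With 8 completers (7 df, critical value 2.365, r = 0.7) they become 9%, 16% and 35%.

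**Step 2: VR significant, control not.** The arms are independent, so this is approximately p(1 − p):

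- g = 0.2: 0.127 × 0.873 = 11%
- g = 0.3: 0.232 × 0.768 = 18%
- g = 0.5: 0.532 × 0.468 = 25%

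**Step 3: at least one of three subtests.** The subtests come from the same 12 people, so independence is not a fair default. Simulating change scores correlated 0.5 (assumed) gives about 28%, 45% and 79% at g = 0.2, 0.3 and 0.5.

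**Step 4: between-arm tests under the same gains.** In simulation with g from 0 to 0.5 and r from 0.7 to 0.9, the post-score t-test, change-score t-test and ANCOVA all rejected 4.8% to 5.3% of the time. A shared gain does not disturb them.

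**Step 5: value of baseline adjustment.** At an assumed true effect d = 0.8 with 12 per arm:

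- Post-score t-test: noncentrality 0.8 × √6 = 1.96 on 22 df, power about 47%.
- ANCOVA: the residual SD shrinks by √(1 − 0.7²) = 0.714, so the effective d is 0.8 / 0.714 = 1.12 and the noncentrality is 1.12 × √6 = 2.74 on 21 df, power about 74%. The formula ignores chance baseline imbalance; a simulation that includes it gave 72%.

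**The case against.** The strongest reply is that the plan contains the right comparison. Between-arm t-tests come first in the Statistics section, the hypothesis is between-arm, and nothing says that a within-arm p-value will support a VR effect. A practice gain is also a real pre-post change, so detecting it is no error against the paired test's own null. All of this stands. A reader might infer that the analysis is wrong as written, or that within-arm results will be presented as benefit. The documents support neither: they leave the role of the paired tests unstated, and that is the whole of the defect.

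Three other limits also stand.

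- **Regression to the mean.** It is tempting to add this to practice and time. The inclusion criteria do not select on cognitive score, so the documents give no ground for it.
- **Three subtests taken as independent.** 1 − (1 − p)³ gives about 33%, 55% and 90%, which overstates the risk when the change scores are correlated.
- **Assumed inputs.** Every probability rests on them. The retests are six months apart, and if the gain were near zero the excess would vanish. Even then, the paired test would not address the between-arm hypothesis.

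Nor is it established that a between-arm result is unlikely. Power for the post-score t-test runs from 22% at d = 0.5 to 80% at d = 1.2, so that depends on an effect size the plan does not state.

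**Conclusion.** The point holds as a free improvement. The plan gives within-arm paired tests the same standing as the tests of its own hypothesis, and names no between-arm test that uses the baseline score. With no VR effect, r = 0.7 and n = 12, the chance of a significant VR-arm gain on one subtest runs from 2.5% with no retest gain to 53% at 0.5 SD, while the between-arm tests stay near 5%. The direction follows from the design; the size depends on gains and correlations that the documents do not give.

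The protection from the between-arm comparison assumes comparable arms. The Statistics section keeps all controls but only VR completers, and defines completion once by the 6-month programme and once by a 12-week programme. Those statements must be reconciled; the change below does not resolve that.

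**What to change.** In Statistics, replace the sentence on paired tests with two statements:

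1. Conclusions about VR rest on the between-arm comparison of 6-month BICAMS scores, adjusted for the baseline score by ANCOVA.
2. Within-arm mean change is reported with a confidence interval, as description only and without p-values.

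The baseline score is already collected, so this needs no extra visits or participants. The loss is some p-values that cannot answer the trial's question; the gain is precision that grows with the pre-post correlation. Whether alternate forms of the memory tests are used is a separate procedural matter on which the documents are silent, and this change does not depend on it.
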